## **4.2 Exclusion Criteria**

- 4.2.1** Pre-menopausal women who are breastfeeding, pregnant or likely to get pregnant during the study period.
- 4.2.2** Prior surgical treatment of the hemorrhagic CCM lesion.
- 4.2.3** Failure to pass MRI safety screening (claustrophobic, metal implant, etc.).
- 4.2.4** Known allergy or intolerance to gadolinium.
- 4.2.5** Severely impaired renal function (eGFR < 60ml/min), active renal disease or status post-kidney transplants.
- 4.2.6** Statin therapy, for any indication, for more than 7 continuous days or greater than 14 total days within 12 months preceding enrollment.
- 4.2.7** Indication to use statin medication for current approved indication, unrelated to CCM.
- 4.2.8** Known allergy or intolerance to statins.
- 4.2.9** Liver dysfunction or active liver disease (including chronic viral hepatitis) defined as baseline serum transaminases levels twice the upper range of normal.
- 4.2.10** Previous diagnosis of skeletal muscle disorders of any cause (myopathy), or baseline creatine kinase levels five times the upper range of normal.
- 4.2.11** Currently treated with or likely to need treatment with one or more of prohibited medications listed in section 5.3.
- 4.2.12** Active drug or alcohol use or dependence that, in the opinion of the site investigator, would interfere with adherence to study requirements.
- 4.2.13** Serious illness (requiring systemic treatment and/or hospitalization) until subject either completes therapy or is clinically stable on therapy, in the opinion of the site investigator, for at least 30 days prior to study entry.
- 4.2.14** Any other condition that the investigator believes would pose a significant hazard to the subject if the investigational therapy were initiated, including conditions resulting in or precipitating myopathy (e.g. HIV, uncontrolled hypothyroidism).

- 4.2.15** In the investigator's opinion, the patient is unstable, and would benefit from a specific intervention rather than treatment with atorvastatin.
- 4.2.16** Inability or unwillingness of subject or legal guardian/representative to give written informed consent.
- 4.2.17** No documentation of valid healthcare insurance.
- 4.2.18** No medical record confirmation of a primary care physician or other provider of ongoing medical care.
- 4.2.19** Previous cranial irradiation or radiosurgical treatment.
- 4.2.20** Use of ritonavir as an oral drug for COVID-19

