## 6.2 Timing of Evaluations

### **6.2.1 Initial screening visit (V0) – up to 30 days prior to enrollment**

This visit may occur on the same day as the baseline visit (V2) at the discretion of the investigator. Subjects will undergo the following assessments and sign an informed consent form in order to be randomized into this study:

- Informed consent
- Obtain subject demographics
- Eligibility criteria (inclusion/exclusion criteria)
- Neurosurgical review (confirmation of diagnosis, date of last symptomatic hemorrhage, statin use, past medical and surgical history)
- Laboratory blood tests (CBC, renal functions, LFT, CK, lipid profile, HIV, hepatitis viral profile and pregnancy test)
- Blood sample processed for ROCK activity assay on peripheral leukocytes, and plasma stored in biobank for future/ancillary biomarker studies.
- Characterization of genotype in cases with multiple lesions, or referral to Angioma Alliance for genotyping through the Alliance's program ([www.angioma.org](http://www.angioma.org)).

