**6.2.5 Twelve month follow-up visit (V5) – 12m +/- 4wks**

The following assessments will be performed on all subjects at 12 months from enrollment:

- Laboratory blood tests (Renal functions, LFT, CK and lipid profile)
- MRI with DCEQP and QSM
- mRS
- Euro-QoL 5D, Euro-QoL VAS, Neuro-QoL SF Cog evaluations
- Intervention adherence/ adverse events review: review results of laboratory investigations, review study monitoring device (eDiary/smart bottle), manual pill count, elicit drug-related adverse events, full medical examination, MMSE, assess suitability for continuation of statin therapy.
- Neurosurgical review: neurological examination, MMSE, discuss results of MRI, dose modification if necessary.
- Blood sample processed for ROCK activity assay on peripheral leukocytes, and plasma stored in biobank for future/ancillary biomarker studies.

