### **6.3.6 Laboratory tests**

These assessments will be performed at the baseline, 12 and 24 month follow up visits prior to every MRI scan according to the study schedule (Table 1) (84, 85). Assessments marked with an asterisk (\*) will also be performed at the 3 month follow up visit as part of the subject's local, routine care to assess statin tolerance:

- **Complete blood count (CBC):** performed as part of baseline blood tests and repeated only if clinically indicated
- **Renal functions\*:** Renal functions and electrolytes, performed at screening to determine subjects baseline renal function and safety of IV contrast material. Repeated prior to every scheduled MRI scan and as clinically indicated. Could be substituted with pin-prick tests prior to IV contrast administration according to local protocol.
- **Liver function tests (LFTs)\*:** liver transaminases, alkaline phosphatase and bilirubin performed at baseline and at 6 months from enrollment on all subjects.
- **Thyroid function tests (TFTs):** performed at screening and when investigating adverse events.
- **Serum creatine kinase (CK)\*:** performed at baseline and at 6 months from enrollment on all subjects.
- **Lipid profile:** Total cholesterol, HDL and LDL.
- **Hepatitis viral profile**
- **HIV** (Known cause of myopathy, which is one of the most common side effects of statins resulting in cessation of treatment).
- **Pregnancy test**
- **Blood sample shall also be drawn for ROCK activity assay on peripheral leukocytes** as detailed in 6.4 below, and plasma freeze-stored for future or ancillary biomarker studies.

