## **7.2 Adverse Event Management Protocol**

Mild adverse events (Table 2, Category A) encountered by any subject regardless of assigned treatment will be recorded, relayed to the safety monitoring team and closely followed by the TN. More concerning adverse events (Category B) will be managed by withholding the study intervention for 2-4 weeks pending resolution of symptoms or biochemical abnormalities. Subjects will then be restarted on the lower dose (40 mg/day) of the study intervention (atorvastatin or placebo). Depending on the dose at which adverse events occurred, the process can be repeated, tapering the dose down to attrition as deemed appropriate by the PI in consultation with the external medical safety monitor (MSM). Intolerable or potentially serious adverse events that recur or persist in spite of dose reduction, along with other serious adverse events listed in Section 8 will lead to unblinding and determination of endpoint for that subject in the trial. A statin expert physician consultant is available at the Chicago site to advise regarding adverse event management in individual cases.

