**7.3.4 Other adverse events.**

Other commonly reported adverse reactions (incidence  $\geq 2\%$  and greater than placebo) regardless of causality, reported in patients treated with atorvastatin in previous placebo-controlled trials, such as nasopharyngitis, diarrhea and urinary tract infection, will be individually reported and managed as elaborated in section 7.2.

**Table 2 below summarizes potential adverse events by body systems that have been reported with the study intervention and other statin medications.**

Adverse Event Category	Mild AE (Category A)	Moderate AE (Category B)	Serious AE (Category C)
General/Constitutional			
• Malaise / Fatigue	Tolerable/self-limited	Intolerable/persistent	Recurrence after dose reduction
• Pyrexia	38.0 - 39.0 degrees C (100.4 - 102.2 degrees F). self-limited	Intolerable/persistent	Recurrence after dose reduction
• Allergic reactions	Erythema multiform	Mild self-limited classic allergic responses such as pruritis, hives or urticaria, cutaneous vasodilation ("flushing"), development of edema (peripheral or airway), peripheral vasodilation (hypotension), bronchospasm, and/or tachycardia.	Recurrence after dose reduction/Anaphylactic reaction/Steven-Johnson syndrome / Toxic epidermal necrolysis
Muscular			
• Musculoskeletal pain (3.5%), muscle spasm (3.6%), arthralgia (6.9%)	Tolerable/self-limited	Intolerable/persistent	Recurrence after dose reduction
• Joint swelling	Asymptomatic; clinical or diagnostic observations only.	Intolerable/persistent	Recurrence after dose reduction
• Incipient Myositis	CK < 3 x ULN, no relevant clinical symptoms.	CK >3 x ULN Plus new elevation of ALT, irrespective of musculoskeletal symptoms.	Recurrence after dose reduction
• Definite Myositis (0.08%)		Myalgia Plus markedly elevated serum creatine kinase >10 x ULN	Recurrence after dose reduction
• Rhabdomyolysis			Myositis Plus evidence of new renal impairment +/- other organ system failure

Adverse Event Category	Mild AE (Category A)	Moderate AE (Category B)	Serious AE (Category C)
• Tendon Rupture			Tendon Rupture
GI/Hepatobiliary			
• Pharyngeal pain (2.3%) , dyspepsia (4.7%), nausea (4%), bloating, eructation, flatulence or diarrhea (6.8%)	Tolerable, self-limited	Intolerable/persistent	Recurrence after dose reduction

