• Hepatitis (0.6%)	Elevated Transaminases (ALT, AST): <ULN - 3.0 x ULN, no relevant clinical symptoms.	Elevated Transaminases (ALT, AST): >ULN - 3.0 x ULN, no relevant clinical symptoms.	Recurrence after dose reduction / ALT >3.0 ULN; >3 x ULN with the appearance or worsening of fatigue, nausea, vomiting, right upper quadrant pain or tenderness, fever, rash, or eosinophilia
• Acute Liver failure			Hepatitis plus abnormal plasma levels of ammonia, bilirubin, lactic dehydrogenase, and alkaline phosphatase
• Cholestasis		Serum conjugated bilirubin >1.5 x ULN; clinical jaundice.	Recurrence after dose reduction
• Pancreatitis			Severe abdominal pain; vomiting plus enzyme elevation (amylase 200 above ULN with elevated lipase levels) or radiologic findings
Nervous System			
• Dizziness, insomnia (3%), Depression, nightmares	Tolerable, self-limited	Intolerable/persistent	Recurrence after dose reduction

Adverse Event Category	Mild AE (Category A)	Moderate AE (Category B)	Serious AE (Category C)
• Cognitive impairment	1 points drop in MMSE; not interfering with work/school/life performance; specialized educational services/devices not indicated	>1 points drop in MMSE; interfering with work/school/life performance; specialized educational services/devices not indicated	Persistence after dose reduction
• Symptomatic Intracerebral Hemorrhage			New onset neurological symptoms Plus intraparenchymal or intralosomal hemorrhage confirmed on imaging studies
Endocrine system			
• Hyperglycemia		New impaired glucose tolerance/glycemic control	Persistence after dose reduction
Respiratory			
• Nasopharyngitis (8.3%)	Tolerable, self-limited	Intolerable/recurrent	Recurrence after dose reduction
• Epistaxis	Mild episode, self-limited	Requiring medical attention, Recurrent episodes	Recurrence after dose reduction
Genitourinary			
• Urinary tract infection (5.7%)	Simple cystitis	Recurrent cystitis /pyelonephritis	Recurrence after dose reduction

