## 8. CRITERIA FOR INTERVENTION DISCONTINUATION

Atorvastatin/Placebo administration will be discontinued for any of the following reasons (designated as serious AEs or Category C in the preceding Table 2):

- Symptomatic intracerebral hemorrhage (ICH) whether primary, arising from index cavernous malformation that previously bled, or in other lesion, or other ICH of any kind
- Severe allergic reaction
- Rhabdomyolysis
- Markedly elevated liver enzymes
- Liver failure
- Pancreatitis
- Pregnancy
- Intolerable adverse events that persist or recur after serial dose reduction.
- In the investigator's judgment, withdrawal from the trial would be in the subject's best interest (Drug interaction/glycemic control).
- The subject or legal representative withdraws consent, or patient undergoes surgical resection or irradiation of CCM lesion, other brain surgery or irradiation for any cause.
- Patient develops clinical indications for statin use for cholesterol or cardiovascular indications unrelated to CCM.

If one or more of these events occur after commencing the study drug, the subject will be considered to have reached a safety endpoint. Study drug or placebo shall be discontinued. All subjects reaching safety endpoints will be followed through the 24-month follow up visit as a part of the outcome assessment for the study. An attempt will be made to contact subjects who withdraw from the study or who are lost to follow up for safety evaluation. If these subjects wish not to cooperate there will be no additional follow up.

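### No scheduled glycemic measure supports the Category B hyperglycemia event, and Table 2 leaves an isolated CK of 3 x ULN or more without a category

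*Combined protocol and SAP*

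**What the plan says.** **Glycemia.** The Hyperglycemia row of Table 2 has an empty Category A cell. Category B is "New impaired glucose tolerance/glycemic control", and Category C is persistence after dose reduction. The row gives no threshold, test or incidence. Section 7.2 sets the consequence of Category B: "More concerning adverse events (Category B) will be managed by withholding the study intervention for 2-4 weeks pending resolution of symptoms or biochemical abnormalities", followed by restart on the lower dose tier. Section 8 lists "Drug interaction/glycemic control" as an example of investigator-judged withdrawal.

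The screening panel in 6.2.1 reads "Laboratory blood tests (CBC, renal functions, LFT, CK, lipid profile, HIV, hepatitis viral profile and pregnancy test". Section 6.2.3 asks for renal function, LFT and CK at 3 months. Section 6.2.5 asks for "Laboratory blood tests (Renal functions, LFT, CK and lipid profile" at 12 months, and 6.2.7 repeats that list at 24 months. Section 6.3.6 describes the renal panel as "Renal functions and electrolytes, performed at screening to determine subjects baseline renal function and safety of IV contrast material".

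**CK.** Table 2 has three CK criteria apart from recurrence and rhabdomyolysis:
- Category A: CK below 3 x ULN without relevant symptoms.
- Category B, incipient myositis: CK above 3 x ULN plus "new elevation of ALT, irrespective of musculoskeletal symptoms".
- Category B, definite myositis: myalgia plus CK above 10 x ULN.

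Exclusion 4.2.10 bars entry at "baseline creatine kinase levels five times the upper range of normal". Section 7.3.2 leaves management of myositis to the principal investigator, according to symptoms and the degree of laboratory elevation, in consultation with the statin consultant.

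**The concern.** The categories in Table 2 are operative. Sections 3.4 and 5.1 tie dose reduction to pre-specified Category B criteria, section 8 ties discontinuation to Category C, and 10.4.1.2 says that serious adverse events broadly correspond to Categories B and C. A risk that is named in the table but not looked for, or a result that the table does not classify, leaves those rules to case-by-case judgment.

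The glycemia gap matters more. Deciding that impairment is new needs a value from before treatment, and deciding that it persists after dose reduction needs values before and after the change. The trial schedules neither. Reports from subjects and outside care will bring in symptomatic or diagnosed cases, but not silent ones. A final table with few or no hyperglycemia events could then be read as reassurance about the drug when it reflects the absence of measurement.

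**Working it through.** The plan states no figure on this point, so the check compares the event definitions with the schedule and then applies the CK rows literally.

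**1. Glycemic measure in each scheduled panel**

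| Time point | Source | Tests listed | Glycemic test |
|---|---|---|---|
| Screening | 6.2.1, Table 1 | CBC, renal, LFT, CK, lipids, HIV, hepatitis, pregnancy (Table 1 adds TFT) | none |
| 3 months | 6.2.3, Table 1 | renal, LFT, CK | none |
| 12 months | 6.2.5, Table 1 | renal, LFT, CK, lipids | none |
| 24 months | 6.2.7 | renal, LFT, CK, lipids | none |

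Sections 5.3.1 and 6.3.6 add none. The result is 0 of 4 time points, so 0 scheduled values in 80 subjects. A local laboratory may print a glucose value with its renal panel, but the plan does not ask for it as trial data.

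**2. Possible number of cases.** Table 2 gives no incidence for this row. Under an assumed two-year incidence of 2% to 10% in the 40 subjects on atorvastatin:
- 40 x 0.02 = 0.8
- 40 x 0.10 = 4

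That is about 1 to 4 subjects, of whom those without symptoms or outside testing would be missed. The range is an assumption without support in the documents.

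**3. CK rows applied literally.** The values tried were 2, 3, 4, 6, 10, 11 and 50 x ULN, each with and without a new ALT rise and with and without myalgia.

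| CK (x ULN) | ALT not newly raised, no myalgia | ALT not newly raised, myalgia | New ALT rise, no myalgia | New ALT rise, myalgia |
|---|---|---|---|---|
| 2 | A | no CK row | A | no CK row |
| 3 | none | no CK row | no CK row | no CK row |
| 4, 6, 10 | none | no CK row | B | B |
| 11, 50 | none | B | B | B |

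Where myalgia is present but no CK row applies, the musculoskeletal pain row can still classify the symptom. In the first column, every value tried from 3 x ULN upward has no category. A value of exactly 3 x ULN fits no CK row in any column.

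**4. Entry limit.** Because 4.2.10 excludes at 5 x ULN, a subject may enroll with an isolated CK between 3 and 5 x ULN, a level that Table 2 does not classify.

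**The case against.** A reader might infer that these rules can never be triggered, that an isolated CK rise leads to no action, or that the by-arm safety comparison is worthless for both risks. The documents do not support any of these.

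- **The CK rules can fire.** CK is scheduled, and both Category B criteria can be met.
- **An isolated CK rise has an action route.** Section 9.1 has the trial nurse contact subjects with relevant laboratory abnormalities and give instructions on continuing, reducing or stopping the drug. Section 7.3.2 adds the judgment of the principal investigator and the statin consultant.
- **CK values reach the analysis.** Section 10.4.1.1 counts an abnormal laboratory finding as an adverse event, 9.4.1 gives laboratory abnormalities by arm to the safety monitor, and 9.5 compares abnormal laboratory data by treatment group. None of this needs a Table 2 category.
- **An entry limit need not equal an on-drug action level.** The 5 x ULN exclusion therefore does not contradict Table 2.
- **Hyperglycemia is not found only by chance.** The row has no laboratory threshold. Medical history is retaken at 12 and 24 months, medications are reviewed at every contact, adverse events are elicited repeatedly, and section 6.3.7 allows other investigations. The pancreatitis and acute liver failure rows also use tests that are not scheduled.
- **The assay would not give a powered comparison.** Even 4 of 40 against 0 of 40 gives a two-sided Fisher p of 0.12.

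All of this stands, and it confines the CK part to a gap in classification. It does not close the glycemia gap. Those routes depend on symptoms, a diagnosis or testing elsewhere. Pancreatitis and liver failure present clinically, whereas early glycemic impairment may not. Section 7.3.3 already accepts the principle for the liver: enzymes are scheduled in order to find symptom-free elevations, although the plan says routine monitoring is no longer required.

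**Conclusion.** The point holds in two parts of unequal weight.

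**Glycemia.** This is a worthwhile, low-cost improvement. None of the 4 scheduled blood time points carries a glycemic measure for an event that the plan itself makes a ground for holding drug, reducing dose and withdrawing. Symptom-free cases are not systematically detected in either arm, and an absence of recorded events would not show safety. The number of cases at stake is unknown. The 1 to 4 subjects above rest on the assumed 2% to 10%. The gain is in ascertainment and in having a baseline, since the trial could not establish a difference at those rates.

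**CK.** This is close to missing detail. With neither a new ALT rise nor myalgia, Table 2 assigns no category to any CK from 3 x ULN upward, so the response rests on judgment under 7.3.2 and 9.1. The values are still measured, monitored and compared by arm.

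Neither part affects the primary endpoint, sample size or power.

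**What to change.** Reconcile Table 1, sections 6.2, 6.3.6 and 7.3.2, section 8 and Table 2 in one amendment:

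1. Add a glycemic measure to blood already drawn at baseline and at existing follow-up draws. Record it as trial data and report it by arm with the other laboratory results in 9.4.1 and 9.5. The 3-month sample is taken through the subject's local care, so the amendment should say which follow-up draws are included.
2. Extend the CK rows so that every result, with or without an ALT rise or symptoms, falls in a stated category, including a value exactly on a boundary and an isolated elevation already present at entry.
3. Leave the choice of assay, all cut-points and all resulting actions to the sponsor's statin consultant and the independent medical safety monitor. No clinical threshold is proposed here.

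The cost is a change to the tables and laboratory lists, one low-cost assay on existing draws, and some incidental abnormal results that will need follow-up in both arms. No extra visit or blood draw is needed.

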**Table 2: Statin-related adverse events.**

AEs are classified based on body system, severity and reported incidences (102, 103, 106-108)

## 8. CRITERIA FOR INTERVENTION DISCONTINUATION

Atorvastatin/Placebo administration will be discontinued for any of the following reasons (designated as serious AEs or Category C in the preceding Table 2):

- Symptomatic intracerebral hemorrhage (ICH) whether primary, arising from index cavernous malformation that previously bled, or in other lesion, or other ICH of any kind
- Severe allergic reaction
- Rhabdomyolysis
- Markedly elevated liver enzymes
- Liver failure
- Pancreatitis
- Pregnancy
- Intolerable adverse events that persist or recur after serial dose reduction.
- In the investigator's judgment, withdrawal from the trial would be in the subject's best interest (Drug interaction/glycemic control).
- The subject or legal representative withdraws consent, or patient undergoes surgical resection or irradiation of CCM lesion, other brain surgery or irradiation for any cause.
- Patient develops clinical indications for statin use for cholesterol or cardiovascular indications unrelated to CCM.

If one or more of these events occur after commencing the study drug, the subject will be considered to have reached a safety endpoint. Study drug or placebo shall be discontinued. All subjects reaching safety endpoints will be followed through the 24-month follow up visit as a part of the outcome assessment for the study. An attempt will be made to contact subjects who withdraw from the study or who are lost to follow up for safety evaluation. If these subjects wish not to cooperate there will be no additional follow up.

